If sufficient quantities of EES and, among them, sufficient mouse paralysis is observed, model-based analyses will be used to supplement the descriptive summaries described above. (See also the section *Alternate Method for Lack of Model Fit*, below.) It is currently known that, prior to the amplification step required to conduct the assay, only 2 post-dose-1 EES are available from the historical control subjects, UAM1. It is therefore likely that model-based analyses will fail, and/or will fail to provide additional insight beyond the descriptive summaries previously described, however, model-based analyses will still be attempted.

For each vaccine group, a generalized linear mixed model (GLMM) will be fitted to the binomial count of paralyzed mice for NEARs obtained at the $4.0 \log_{10} \text{CCID}_{50}/\text{g}$ dose level. This model is given by

$$\text{logit}^{-1}(p_i) = \beta_0 + \beta_1 I_{[\text{sex}=\text{F}]} + \delta_i \quad (1)$$

where

- β_0 is the overall mean log-odds of paralysis for male mice
- β_1 is the difference in mean log-odds of paralysis between mouse gender (females minus males)
- p_i is the paralysis rate for sample (subject) i
- $\delta_i \sim N(0, \tau^2)$ is the subject-level random effect, intended to capture overdispersion due to between-sample variability in the neurovirulence of each virus population, including variability in the precise titer of inoculum

In SAS/STAT software, this model may be fitted using the PROC GLIMMIX procedure. It is preferred to use METHOD = LAPLACE in the PROC GLIMMIX statement, due to better asymptotic performance of the estimators. The SAS default method for computing degrees of freedom should be utilized for statistical tests (DDFM = BETWITHIN). SAS code to fit the model defined above is given by:

```
proc glimmix data=dat method=laplace;
  class sample sex;
  model x/n = sex / cl solution ddfm = betwithin;
  random intercept / subject=sample;
  lsmeans sex / ilink;
run;
```

where “sample” is the sample number (e.g., subject identifier providing the sample), “x” is the mouse gender-specific number of mice paralyzed, “n” is the mouse gender-specific number of

inoculated mice available for analysis, and “sex” captures the mouse gender. The dataset “dat” should contain one row for each subject, for each mouse gender. Additional options to the SAS procedure may be necessary to obtain all necessary output.

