Model fit results should be summarized in a table, including coefficient estimates and standard errors, p-values from *t*-tests of coefficients, and 95% confidence interval (based on the *t* distribution, the default for PROC GLIMMIX); similarly for the variance component. P-values for variance components will be based on the likelihood ratio test described by Molenberghs and Verbeke [2]. Additionally, the estimated mean paralysis rate per gender at the nominal dose level (4.0 log₁₀ CCID₅₀/g), will be obtained by inverting the logit transformation, and the delta method will be used to obtain its standard error, from which the 95% confidence interval will be obtained, utilizing asymptotic normality, and truncated at (0, 1) if necessary. A SAS LSMEANS statement will be used to obtain log-odds of paralysis averaged over mouse gender, and the corresponding probability and its 95% CI will be obtained via these same methods.

In the event that the multiple-dose format of the assay is employed for samples from one or more subjects, due to an excessive number of mice paralyzed (as defined in [1]):

1. The methods above will be employed, omitting the additional dose levels tested for those subject(s) *with* additional dose levels tested
2. The methods will be augmented with the analyses described in the *Statistical Methods for Multi-dose Assays* section below

Statistical Methods for Multi-dose Assays

In the event that the multiple dose format of the assay is employed for samples from one or more subjects, the GLMM described in (1) above will be augmented with a term for dose level as a continuous variable, and the NEARs will be modeled as:

$$\text{logit}^{-1}(p_{ij}) = \beta_0 + \beta_1 D_{ij} + \beta_2 I_{[sex=F]} + \delta_i \quad (2)$$

where

- β_0 is the overall mean log-odds of paralysis for male mice
- β_1 is the change in log-odds of paralysis associated with a unit increase in dose level of inoculum
- β_2 is the difference in mean log-odds of paralysis between mouse gender (females minus males)
- p_{ij} is the paralysis rate for sample *i* at dose level *j*
- D_{ij} indicates the *actual* (as opposed to nominal) dose level for sample *i*, indexed by *j*

- $\delta_i \sim N(0, \tau^2)$ is the subject-level random effect, intended to capture overdispersion due to between-sample variability in the neurovirulence of each virus population

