It is expected that candidate vaccines will produce virus populations with low neurovirulence, and therefore it is possible that very few mice are paralyzed at the fixed dose level of inoculum (4.0 \log_{10} CCID₅₀), or at lower dose levels for either or both vaccine candidates. It is also possible that few subjects shed virus in sufficient quantity to enable the assay to be conducted. In either case, it is possible that the GLMM described above may not be able to be fitted to the data. In the event that paralysis proportions are low, the variance component will be difficult to fit. If the model is unable to be fitted using SAS default values for optimization convergence criteria, the following methods will be employed, in sequence, as backup:

1. The GLMM model will be reduced to a GLM model, by omitting the variance component term, and all methods above will be used. This method ignores the overdispersion expected by combining data from heterogeneous virus populations obtained from different subjects but will produce reliable estimates of mean paralysis rates if the contributions from each subject (sample size of mice) are relatively balanced, which is expected here. In this case, statistical inference would be affected, but the analysis is intended to be descriptive, rather than inferential.
2. In the event that 1) above fails to fit (due, for example, to *no* observation of paralysis), then all analysis will be limited to the descriptive analyses presented above equation (1)

Comparative Analysis for OPV-vaccinated subjects

In order to compare the neurovirulence of shed virus between each candidate vs the control, the following model will be fitted:

$$\text{logit}^{-1}(p_{hi}) = \beta_0 + \beta_1 I_{[h=2]} + \beta_2 I_{[sex=F]} + \delta_i \quad (3)$$

where

- h indexes virus ($h = 1$ = control vaccine [M1], $h = 2$ = candidate vaccine [M4])
- i indexes sample (subject) within levels of h
- β_0 is the overall mean log-odds of paralysis for shed virus samples for male mice, control vaccine
- β_1 is the difference in mean log-odds of paralysis between the two vaccines
- β_2 is the difference in mean log-odds of paralysis between mouse gender (females minus males)
- p_{hi} is the paralysis rate for virus source h , sample i

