Model fit results should be summarized in a table, including coefficient estimates, standard errors, p-values for *t*-tests of coefficients, and 95% confidence interval (based on the *t* distribution, the default for PROC GLIMMIX) will be displayed for coefficients as well as for the variance components. For each candidate vaccine, the odds ratio (paralysis in each candidate vaccine group relative to the control group from study M1) and its corresponding two-sided 95% CI and two-sided p-value will be presented. P-values for variance components will be based on the likelihood ratio test described by Molenberghs and Verbeke [2]. Additionally, the estimated mean paralysis rate for each virus source h , \widehat{p}_h , will be obtained from the results of the SAS LSMEANS statement, and the delta method will be used to obtain the standard error, from which the 95% confidence intervals will be obtained, utilizing asymptotic normality, and truncated at (0, 1) if necessary. The odds ratio of paralysis between mouse genders, assumed common among vaccines groups, will also be presented as described for the gender-averaged probability.

As with other model-based methods above, if the model cannot be fit, remedies involve stepwise model simplification. For this model, the first simplification will be to reduce from a GLMM to a GLM via removal of the variance component. If that model cannot be fit, results will be limited to presentation of summaries described above equation (1) and augmented with the two-sided Fisher exact p-value arising from the cross-tabulation of paralyzed mice within each group, regardless of mouse gender and subject identifier, and the p-value will be regarded as approximate. If substantial imbalance in mouse availability rate is observed, additional sensitivity analyses may be added.

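### The 95% interval for the mouse paralysis rate is formed on the probability scale, so its upper limit is too low at low but non-zero paralysis; the mean-rate label is also ambiguous

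*SAP*

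**What the plan says.** SAP 6.7.2, Model-based Analyses: "For each vaccine group, a generalized linear mixed model (GLMM) will be fitted to the binomial count of paralyzed mice" at the single nominal dose, with mouse sex as a fixed effect. The model has a normal random intercept per sample, which "is the subject-level random effect, intended to capture overdispersion due to between-sample variability in the neurovirulence of each virus population". The quantity labelled the estimated mean paralysis rate "will be obtained by inverting the logit transformation". Its uncertainty is taken from the delta method, and limits are then set on the probability scale: "from which the 95% confidence interval will be obtained, utilizing asymptotic normality, and truncated at (0, 1) if necessary". For the rate over both sexes, "A SAS LSMEANS statement will be used to obtain log-odds of paralysis averaged over mouse gender", and the same steps follow. No step integrates over the random effect.

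The Comparative Analysis for OPV-vaccinated subjects builds the interval for each virus source in the same way: "utilizing asymptotic normality, and truncated at (0, 1) if necessary".

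The Alternate Method for Lack of Model Fit anticipates that "it is possible that very few mice are paralyzed at the fixed dose level of inoculum" and that the variance component is then hard to estimate. If the mixed model cannot be fitted, the random effect is dropped and the remaining methods, including this interval, are kept. If that also fails, for example because no mouse is paralysed, only the descriptive summaries remain.

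**The concern.** A rate near zero has a skewed sampling distribution. A symmetric interval around it reaches below zero on one side and stops short on the other. For a vaccine meant to show low neurovirulence, the upper limit is the side a reader will look at, and an error there makes the virus look safer than the data show. Protocol 1.2.2.1 names reduced reversion to virulence as one of three criteria for eventual licensure, so these figures will be read even though the analysis is exploratory.

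The point estimate raises a second question. In a logistic model with a random intercept, inverting the logit of the fixed effects gives the rate for a sample at random effect zero. That is not the mean over samples unless the between-sample variance is zero or the rate is 50%.

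**Working it through.** **Inputs.** The documents give no paralysis rate, number of mice, number of qualifying candidate samples or between-sample SD (tau), so the plan has no figure of its own to reproduce. All such values below are assumptions. The binomial work pools the sexes and uses 1.96 for both intervals, so the comparison is of scale only.

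**1. The two intervals for x paralysed of N, no clustering.** With p = x/N, SE(logit) = √(1/x + 1/(N − x)).
- Planned: p ± 1.96 × p(1 − p) × SE(logit), cut at 0 and 1.
- Logit scale: expit(logit p ± 1.96 × SE(logit)).

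For 2/40: p = 0.05 and SE(logit) = √(1/2 + 1/38) = 0.7255.
- Planned: delta SE = 0.05 × 0.95 × 0.7255 = 0.0345; limits 0.05 ± 0.0675 = −1.8% to 11.8%, reported as 0 to 11.8%.
- Logit scale: −2.944 ± 1.422, giving 1.3% to 17.9%.
- Exact (Clopper-Pearson) upper limit: 16.9%.

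Upper limits at other counts:

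| Paralysed / mice | Planned | Logit scale | Exact |
|---|---|---|---|
| 1/100 | 2.95% | 6.75% | 5.45% |
| 2/100 | 4.7% | 7.6% | 7.0% |
| 5/100 | 9.3% | 11.5% | 11.3% |
| 10/100 | 15.9% | 17.6% | 17.6% |

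**2. How often the true rate lies above the upper limit** (exact binomial, given at least one paralysed mouse; nominal 2.5%). At N = 100 and a true rate of 5%, the planned limit misses when x is 1 or 2. P(1) + P(2) = 0.0312 + 0.0812 = 0.1124; dividing by 1 − 0.0059 gives 11.3%.

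| Mice, true rate | Planned: true rate above upper limit | Planned: true rate below lower limit | Logit: true rate above upper limit |
|---|---|---|---|
| 100, 5% | 11.3% | 0.4% | 0% |
| 200, 2% | 7.3% | 0.3% | 0% |
| 400, 2% | 9.7% | 0.8% | 1.3% |

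At 100 mice and 5%, two-sided coverage is 100 − 11.3 − 0.4 = 88.3% for the planned interval. For the logit interval, which misses below 2.8% of the time, it is 97.2%.

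**3. Where the problem stops.** With one paralysed mouse the planned upper limit is about (1 + 1.96)/N = 2.96/N. If fewer than about 3 paralysed mice are expected, no fitted result can put the upper limit below the true rate. At the other end, the upper-side miss falls to 3.6% at N = 400 and a rate of 10%.

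**4. With clustering.** An intercept-only version of the model was simulated with 5, 10 or 20 samples of 20 mice, tau = 1, a typical-sample rate of 2% or 5%, and 600 runs per setting. The planned upper limit fell below the typical-sample rate in 5.5% to 8.6% of fits, against 0 to 0.3% on the logit scale.

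**5. Typical-sample rate against population mean.** The reported value is expit(b); the population mean is the average of expit(b + tau × Z) over standard normal Z. For a typical-sample rate of 5%, the mean is 5.5%, 7.3% or 10.1% for tau of 0.5, 1 or 1.5. At tau = 0 the two are equal.

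**The case against.** Neurovirulence is an exploratory endpoint. No threshold or decision in the SAP uses this interval, and the SAP calls the analysis descriptive where it discusses the fallback. The count and percent of paralysed mice are summarised by vaccine group whatever happens to the models, and that pooled percent has no conditional shift. Logit-scale coefficients with their intervals, and the variance component, are tabulated too. The comparison with UAM1 rests on an odds ratio that does not use the delta interval. All of this stands and keeps the point small.

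It can also be said that the models will probably fail. The SAP says so, but bases this on only two post-dose-1 qualifying samples from UAM1. That limits the comparative model. The non-comparative model is fitted to each vaccine group separately, is planned for the IPV-vaccinated groups as well, and is to be attempted in any case.

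A reader might infer three stronger things that the documents do not support:

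- **Truncation at 0 causes the error.** A rate cannot be negative, so clipping loses no coverage. Truncation is a symptom of symmetry on the wrong scale.
- **Interval and mean are both too low whenever paralysis is rare.** The mean shift needs a mixed model fitted with tau above zero. The SAP expects the variance component to be difficult when paralysis is low, and plans a model without it. In the simulation above, tau was estimated at 0 in 37% to 57% of fits with 5 samples and 18% to 40% with 10.
- **The rarer the paralysis, the worse the coverage.** Step 3 shows otherwise, and with no paralysis no model interval is expected.

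**Conclusion.** The concern holds in two limited parts.

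**Interval.** The construction is on the wrong scale in the mixed model, the comparative model and the fallback without a random effect. At low but non-zero counts the upper limit is too low: 11.8% against 17.9% (16.9% exact) for 2/40. When roughly 4 to 8 paralysed mice are expected, the true rate lies above the limit about three to four and a half times as often as it should (7.3% to 11.3% against 2.5%). The misses fall almost entirely on the side that understates neurovirulence.

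**Label.** Only when the mixed model is fitted with tau above zero is the reported mean a typical-sample rate. Under the fallback, or with tau estimated at zero, it coincides with the population mean. The same label can therefore denote different quantities for different vaccine groups, depending on how each fit went, and the SAP does not say so. The size of the shift depends wholly on tau, which is unknown.

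Every mouse number, rate and tau here is assumed, and the figures in steps 1 and 2 ignore clustering. This is a minor point that corrects error bars. It does not touch the trial's primary or secondary conclusions.

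**What to change.** In SAP 6.7.2, replace the delta-method normal interval with limits computed on the logit scale and back-transformed, both under Model-based Analyses and under the comparative analysis. The fallback, which reuses those methods, then follows. In the code for model (1), add CL to the LSMEANS statement that already has ILINK, and use the same options wherever the sex-averaged log-odds is requested. The code for model (3) already asks for both. The truncation clause then becomes unnecessary.

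Add one sentence that labels the mixed-model estimate as the typical-sample (conditional) rate, or also report the rate integrated over the random effect. State for each group whether the mixed model or the fallback was used.

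The cost is one SAS option and a sentence or two; integrating over the random effect would need a short extra computation. There is a small downside: logit limits are somewhat conservative at very low counts, for example 6.75% against 5.45% exact for 1/100.

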8.4 EXPLORATORY EVALUATIONS

8.4.1 *Neurovirulence*

As noted above, a pre-specified subset of the stool samples collected for viral extraction (as outlined in the Time and Events schedule) will be analyzed by PCR and cell culture infectivity (CCID50). Of these, a further subset will be assessed for neurovirulence and genetic sequence.

For the neurovirulence testing of virus derived from stool samples of clinical trial participants vaccinated with oral polio vaccines, a modified transgenic mouse neurovirulence test (mTgmNVT) may be applied. The TgmNVT that will be used is adapted from the WHO SOP (Neurovirulence Testing of Oral Polio Vaccine Using TgPVR21 Transgenic Mice) used for vaccine release.

In the mTgmNVT, blinded, cell culture-amplified virus material (from stool) is titrated and then diluted to a fixed target dose/inoculum selected to detect reversion of the Sabin-2 strain. The inoculum is intraspinally injected into transgenic mice susceptible to poliovirus. Control virus is tested concurrently in the TgmNVT to assess the validity of a given test.

The inoculated mice are observed daily for the presence of clinical signs of poliovirus infection (weakness, paresis, and paralysis). After the observation period of 14 days, the in-vivo phase is ended. Mice are euthanized and a clinical end score (paralyzed or non-paralyzed) is assigned to each mouse. Results are reported as percent paralysis observed per sample. Samples that induce paralysis above a critical threshold may be further tested in a multi-dose format of the TgmNVT for further characterization.

NV data from this study may be combined with data from prior studies to further optimize this assay and also to draw comparisons between shed virus from Sabin-2 and the novel vaccine candidates.

8.4.2 *Sequencing*

Viral sequencing methods (e.g. deep sequencing) will be performed on selected stool samples taken at one or more of the time points specified in the Time and Events schedule to explore the heterogeneity of shed virus. Sequence information on shed virus may be compared with the results of neurovirulence testing, if available.

8.4.3 *Further exploratory work.*

Serum or stool samples that remain after protocol-specific assessments have been performed may be used for further exploration of safety lab parameters, and/or exploratory work on polio for maximum 10 years after study closure. No human DNA or RNA analysis will be performed.

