A neurovirulence endpoint assay result (NEAR) is defined as an assay result for a given EES and dose level of inoculum such that the accompanying high- and low-dose controls and the back-titration of inoculum are all within acceptable limits, per SOP. Each subject with a sample tested is anticipated to have 1 NEAR at the nominal single dose level of $4.0 \log_{10} \text{CCID}_{50}/\text{g}$. Additional NEARs at additional dose levels may also exist if the multidose format of the assay is initiated for a given subject/sample.

Assay results will be listed, including subject ID, vaccine group, study day of stool sample assayed, assay repeat number, the back-titration of inoculum, the nominal dose level of inoculum, the total number and percent of mice evaluable and paralyzed (also separately by mouse gender), the count and percent of accompanying high-and low-dose control mouse paralysis, a flag indicating if the assay lead to a re-test, a flag indicating if the assay lead to initiation of the multi-dose format of the assay, and a flag indicating whether the sample is a NEAR.

For NEARs, the number of mice evaluable for scoring as well as the number and percent of these mice paralyzed at each dose level tested (in the event multiple dose levels are used to inoculate groups of mice with a virus population obtained from a single subject) will be summarized (overall as well as by mouse gender), within vaccine group across subjects.

A boxplot of paralysis proportions will be prepared for each vaccine group wherever >2 subjects per dose level are available. Only NEARs using the $4.0 \log_{10} \text{CCID}_{50}/\text{g}$ dose level will contribute to this summary. Points will be overlaid on the boxplots.

Reasons for any sample re-runs, or initiation of the multi-dose format of the assay will be provided in a listing.

Model-based Analyses

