In SAS/STAT software, this model may be fitted using the PROC GLIMMIX procedure. It is preferred to use METHOD = LAPLACE in the PROC GLIMMIX statement, due to better asymptotic performance of the estimators. The SAS default method for computing degrees of freedom should be utilized for statistical tests (DDFM = BETWITHIN). SAS code to fit the model defined above is given by:

```
proc glimmix data=dat method=laplace;
  class sample sex;
  model x/n = dose sex / cl solution ddfm = betwithin;
  random intercept / subject=sample;
run;
```

If only one subject for either vaccine group is available, then the random intercept term will be omitted. If subject numbers are low (e.g., ≤ 3), the GLMM may fail to fit due to numerical instability regarding the variance component. In this case also, the random intercept term will be omitted. Additional options to the SAS procedure may be necessary to obtain all necessary output.

Model fit results will be summarized in a table, including coefficient estimates and standard errors, p-values from t -tests of coefficients, and 95% confidence intervals for coefficients (based on the t distribution, the default for PROC GLIMMIX) as well as the variance component. P-values for variance components will be based on the likelihood ratio test described by Molenberghs and Verbeke [2]. Additionally, the fitted curve(s) will be plotted and accompanied by a descriptive legend, with important features such as the PD_{50} denoted in text on the plot. One curve for each subject will be shown (using estimates of the random effect terms), along with the mean curve in the case of more than 1 subject.

If any dose level produces $\geq 50\%$ of mice paralyzed, the estimated dose level corresponding to a 50% paralysis rate (PD_{50}) will be computed using inverse-prediction from the estimated model, omitting any variance components. The delta method and an assumption of asymptotic normality will be used to compute and present the standard error of this value and an accompanying 95% confidence interval, using Normal distribution critical values.

Alternate Method for Lack of Model Fit

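### In the multi-dose neurovirulence model, the fallback for few samples drops the sample term and puts nothing in its place, so the dose slope and PD50 can be biased when samples differ and only some are multi-dosed

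*SAP*

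**What the plan says.** All of this is in SAP 6.7.2 unless stated.

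- **Who gets extra doses.** Each tested sample is expected to have one valid result at 4.0 log10 CCID50. Beyond that, "Additional NEARs at additional dose levels may also exist if the multidose format of the assay is initiated for a given subject/sample". The trigger in the SAP is "due to an excessive number of mice paralyzed", with the definition left to the assay SOP. Protocol 8.4.1 puts it this way: "Samples that induce paralysis above a critical threshold may be further tested in a multi-dose format of the TgmNVT for further characterization".
- **The model.** Model (2) regresses the log-odds of paralysis on actual dose and mouse sex, with a random intercept per sample. It pools single-dose and multi-dose samples of a group.
- **The fallback.** With one subject the random intercept is left out. The SAP then turns to small groups: "If subject numbers are low (e.g., ≤ 3), the GLMM may fail to fit due to numerical instability regarding the variance component". Its remedy for such a failed fit is the same as for one subject: "In this case also, the random intercept term will be omitted".
- **The outputs.** PD50 comes from inverse prediction with a delta-method interval. The plot is to show a curve for each subject, built from the estimated random effects, plus a mean curve.
- **The defence.** The subsection on lack of model fit accepts that a model without the variance component ignores overdispersion. It calls the estimated mean paralysis rates reliable if subjects contribute similar numbers of mice, and calls the analysis descriptive.
- **The control group.** Before amplification, "only 2 post-dose-1 EES are available from the historical control subjects". The SAP adds that model-based analyses will probably fail or add little.

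**The concern.** A sample is multi-dosed because of its own result at 4.0. The more virulent samples therefore supply all the results at other doses, and the less virulent ones appear only at 4.0. A sample term absorbs that difference. Without one, a change in dose is also a change in the mix of samples, and the fitted slope combines the two.

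The SAP's defence does not reach this. It concerns mean paralysis rates under balanced contributions. Slope and PD50 are not mean rates, and the multi-dose format unbalances the contributions by design.

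The fallback also cannot produce one of its own outputs: once the random effects are gone, no subject-specific curves are left to plot. PD50 and these curves are how the plan describes a sample with unusual paralysis, which is the event that starts this analysis.

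**Working it through.** **No plan figure to reproduce.** The documents give no slope, PD50, mouse number, trigger value or dose grid for this assay.

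**Assumptions.** 20 mice per sample and dose; true slope 1.5, 2 or 3 logits per log10 dose; extra doses 3.0 and 2.0 (5.0 and 6.0 as the alternative); mouse sex balanced and left out. Expected counts were fitted by maximum likelihood.

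**Formulas.** Fallback: logit(p) = a + bD, PD50 = −a/b. Fixed sample effect: logit(p) = a_i + bD, PD50_i = −a_i/b.

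**Mechanism, true slope 2.** Sample A has PD50 3.0, so it paralyses 88%, 50% and 12% at doses 4, 3 and 2. Sample B has PD50 5.0 and is tested only at 4, where it paralyses 12%. Ignoring sample, dose 4 shows (88 + 12)/2 = 50%, dose 3 shows 50% and dose 2 shows 12%. Dose appears to do nothing between 3 and 4. The fitted slope is 0.78 and PD50 3.80, which is neither sample's value.

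**Results without a sample term** (true slope 1.5 / 2 / 3; PD50 in log10):

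| Paralysis at 4.0 and design | Fitted slope | Fitted PD50 | Mean of sample PD50s |
|---|---|---|---|
| 88%, 12%; first also at 3.0 and 2.0 | 0.38 / 0.78 / 1.47 | 3.54 / 3.80 / 3.95 | 4.00 |
| 88%, 73%; first also at 3.0 and 2.0 | 1.19 / 1.65 / 2.53 | 2.74 / 3.10 / 3.43 | 3.00 / 3.25 / 3.50 |
| 88%, 12%, 12%; first also at 3.0 and 2.0 | 0.06 / 0.45 / 1.10 | 10.0 / 4.85 / 4.41 | 4.44 / 4.33 / 4.22 |
| 95%, 82%; both at 3.0 and 2.0 | 1.34 / 1.80 / 2.74 | 2.50 / 2.87 / 3.25 | 2.50 / 2.88 / 3.25 |
| Two equal samples | unbiased | unbiased | – |
| 88%, 12%; first also at 5.0 and 6.0 | 3.19 / 3.79 / 4.92 | 4.00 | 4.00 |

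The first row is about half to three quarters too flat, the second 16% to 21%, the fourth 9% to 11%. If the 88% and 12% samples were both multi-dosed, the slopes would be 0.89 / 1.28 / 2.02 (33% to 41% too flat) with PD50 within 0.06 of the mean, but a 12% sample is unlikely to meet a trigger for excessive paralysis. A fixed intercept per sample recovers the true slope in every row.

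**How often the fallback would be reached.** In simulated two-sample groups (slope 2, sample PD50s normal around 3.8, extra doses only if at least half the mice were paralysed at 4.0, one of the two samples multi-dosed), a random-intercept model was fitted by quadrature. A near-zero variance estimate served as a proxy for instability. It occurred in about 31%, 8% and 6% of groups at a between-sample PD50 SD of 0.4, 0.8 and 1.2 log10. In those groups the PD50 error was about the same with or without a fixed sample term. SAS with the Laplace method may behave differently.

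**An illustrative data set.** Sample A: 19, 14 and 5 of 20 at doses 4, 3 and 2. Two others: 3/20 and 2/20 at dose 4. Without a sample term: slope 0.12, PD50 5.8 (95% CI −5.2 to 16.9). With fixed sample effects: slope 2.0, PD50s 2.6, 4.9 and 5.1. But the random-intercept model also fits these counts, with slope about 1.9 and sample SD about 2.7, so the fallback would probably not be used here.

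**The case against.** The strongest reply is that the rule limits itself. The random intercept goes only when the mixed model cannot be fitted. In the simulation that happened mostly when the samples were alike, which is when dropping it does least harm. Where samples differ greatly, as in the illustrative data, the mixed model fits and nothing is dropped. This stands, and it means the largest distortions in the table should not be read as typical of the fallback.

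It also stands that the analysis is descriptive, that the listings show each sample's paralysis by dose, and that the nominal-dose analysis is kept without the extra doses. A virulent sample would remain visible.

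A fixed sample effect has its own weakness. A sample with no paralysed mice has no finite intercept, and the SAP expects little paralysis. A single-dose sample's PD50 is also an extrapolation along a borrowed slope. Both points limit what should be reported, as the fix does.

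A reader might infer three stronger things that the documents do not support:

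- **That a flattened Sabin curve is the expected outcome for UAM1.** The SAP gives only the count of two samples before amplification. Nothing says that either will be multi-dosed, still less exactly one of them.
- **That the slope must be too flat.** The documents do not fix the extra doses. The SAP's only hint is the phrase "or at lower dose levels for either or both vaccine candidates".
- **That the comparison with Sabin is compromised.** Model (3), which makes it, has no dose term. No passage makes the UAM1 PD50 a benchmark.

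What the reply leaves unanswered: nothing replaces the dropped term, the balance argument does not cover slope or PD50, and the per-subject curves cannot be produced.

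**Conclusion.** The point holds as a narrow gap in an exploratory analysis. If the mixed model cannot be fitted with two or three samples, the stated fallback can bias the dose slope and PD50 when samples differ and only some are multi-dosed. Under the assumed inputs the slope error runs from nil (equal samples), through about 10% (two highly paralysing samples, both multi-dosed) and 16% to 21% (88% and 73%, one multi-dosed), to half or more when samples are far apart, a case in which the mixed model would usually fit. PD50 can move in either direction, or hardly at all.

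These sizes rest on assumed mouse numbers, slopes, trigger and doses. For UAM1 the situation is possible but not shown to be expected. The missing per-subject curves follow from the text alone and need no assumption.

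**What to change.** In SAP 6.7.2, Statistical Methods for Multi-dose Assays, replace the omission rule for more than one sample. When the random intercept cannot be fitted, enter sample as a fixed class effect (`model x/n = sample dose sex`), or fit each multi-dosed sample separately. Report the curve and PD50 for each multi-dosed sample only, and report no pooled PD50 from a model without a sample term. Leave the sample term out only when a single sample exists.

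The cost is a line of text and code, one degree of freedom per extra sample, and no group-level PD50 in this fallback. No new data are needed.
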